## **Study Design**

The social exergame app, Go&Grow, could provide physical, social, and health benefits for family caregivers because of its simple interface for physical activity-related gamification (flowers can be selected and will grow based on the user's completion of daily step goals) and social contact features (users can post stories, share virtual gardens, and react to other users' stories). Participants could also follow workout tutorials implemented to Go&Grow from the National Institute of Health (NIH) Go4life (National Institute on Aging at NIH, 2020), and log and track their workouts on a daily and weekly basis (Figure 2). More details on the description of the full Go&Grow app can be found in the Lin et al., 2020 paper. Each day, the app sent notifications

to remind participants to use the app and asked participants to rate their daily mood using a mood slider.

The treatment group (social exergame condition) used the full version of Go&Grow with the social contact features, which allowed users to view, like, reply to, post a story, and view other users' gardens. They also received in-game rewards (unlock new flowers to grow each week) if they posted stories. The control group (exergame non-social condition) used Go&Grow without the social contact features; therefore, they were not able to unlock new flowers (Figure 2).

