### **Procedure**

The current study was a two-armed randomized control trial with a pretest (baseline week 1 and 2), weekly assessments at the end of each week (week 1 to 8), and a posttest (after week 8). All participants were blinded to their conditions. Both groups received the same frequency of contact from researchers and followed the same procedures throughout the study period.

All contact and data collection were done remotely. Participants who were interested in joining the study were instructed to fill out an online screening form which included the screening items for inclusion and exclusion criteria. If participants were eligible based on the screening, a research assistant reached out to the participant within three days to obtain informed consent. Participants received a copy of the informed consent through email during the informed consent process. Research assistants went over the informed consent with participants over the phone and participants provided consent orally. Once participants agreed to take part in the study, research assistants sent participants a link to complete the demographic survey (including covariates) and the pretest. Upon completion of the demographic survey and the pretest, participants were shipped a Fitbit Inspire 2 tracker, instruction materials, a face mask, and a stylus pen to their home postal address.

**Session 1 (Pretest).** A research assistant trained the participants in both conditions to use the Fitbit by phone and with an instructional manual, an approach that has been effective in previous studies (Bisson et al., 2021; Robinson et al., 2019).

**Week 1-2 (2-Week Baseline).** Participants in both conditions would wear the Fitbit for two weeks to obtain baseline steps. Both conditions also completed a weekly survey for weeks 1 and 2. Each measure collected during this period was averaged to create a baseline score.

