**Week 3 – 8 (6-Week Intervention Period).** On the first day of week 3, research assistants trained participants on how to use Go&Grow with the instructional guide and phone consultation for both conditions. After the training, participants in both conditions started using the app while continuing to wear the Fitbit for 6 weeks. They were reminded daily with app-based notifications to wear their Fitbit and use the Go&Grow app. The reminder for the treatment condition also included the message: “Don’t forget to share your stories to unlock new flowers”. Participants continued completing weekly surveys for 6 weeks.

**After week 8 (Posttest).** All participants completed a posttest, which was the same as the pretest.

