## **Data Analyses**

First, we examined all baseline characteristics between both conditions and all three cohorts. To test the research questions, multilevel models (MLM) and the R package lme4 were utilized. Analyses were conducted for the full sample with intent to treat for everyone who completed the pretest (N=76), as missing data in outcome variables could be handled through multilevel analysis. Sensitivity analyses were also conducted for those who had completed both the pretest and posttest, and those results are shown in the tables in the supplementary. Changes in well-being (loneliness, stress, affect, each subscale of caregiver's stress), physical activity (percent change in the number of steps from baseline to the intervention, MCID, minutes active, and each subscale for the self-reported physical activity), and social support (overall social support and each subscale of social connectedness scale), were examined with a 2 (condition) by 2 (time) analysis examining whether the treatment and control conditions differed in the amount and direction of change from the pretest to the posttest controlling for the covariates. We also explored whether there was a condition by time interaction in secondary outcomes for exercise self-efficacy, life satisfaction, and sense of control. In order to conduct more sensitive analyses, we also did planned comparisons because of our *apriori* predictions. Furthermore, multilevel models were tested to examine whether usage of the social features of the app for the treatment group predicted changes in physical activity. Using the PROCESS Macro model in SPSS (Hayes, 2013), mediation models were tested for mechanisms of change for whether increased social support and physical activity in turn led to better well-being. Covariates including app use were included in all mediation models.

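### App use, which begins after randomisation, is a covariate in every mediation model; where condition is the predictor and app use sits in the mediator equation, any effect running through app use drops out of the indirect effect

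*Combined protocol and SAP*

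**What the plan says.** All statements are in the combined protocol and SAP.

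- **Mediation models (Data Analyses).** Using PROCESS, "mediation models were tested for mechanisms of change for whether increased social support and physical activity in turn led to better well-being". The covariate rule follows: "Covariates including app use were included in all mediation models". The section does not name the predictor, define app use (overall use or use of the social features), say which equations hold the covariates, or mention a mediation analysis without app use.
- **Timing (Participants; Procedure).** Participants counts pretest completers among people already randomised. Procedure places app training on the first day of week 3, and then: "After the training, participants in both conditions started using the app while continuing to wear the Fitbit for 6 weeks".
- **Differences between arms (Study Design; Procedure).** Of the treatment arm: "They also received in-game rewards (unlock new flowers to grow each week) if they posted stories". The control arm "used Go&Grow without the social contact features; therefore, they were not able to unlock new flowers". The treatment arm's daily reminder carried an added prompt to share stories.
- **What was alike (Procedure).** "Both groups received the same frequency of contact from researchers and followed the same procedures throughout the study period". Of both arms: "They were reminded daily with app-based notifications to wear their Fitbit and use the Go&Grow app".
- **A related analysis (Data Analyses).** Multilevel models tested whether "usage of the social features of the app for the treatment group predicted changes in physical activity".

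**The concern.** A covariate in a mediation model with a randomised predictor should normally be fixed before the intervention can act on it. App use is not: it exists only from week 3, and rewards and prompts tied to posting give the treatment arm extra reasons to open the app. The plan's own analysis of social-feature use treats use as a possible driver of physical activity, which is one of the mediators. A path from condition to app use to mediator to well-being is therefore plausible on the plan's own terms, and holding app use fixed in the mediator equation removes it.

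At stake is the mechanism claim. A reader would take the reported indirect effect as the whole effect through support or activity, when it may be only the part that does not pass through app use. If the app-use measure counts social actions such as posting, the adjustment also holds fixed part of what the treatment arm was given.

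**Working it through.** The plan states no figure to reproduce. The check is the order of events, then path algebra with assumed coefficients.

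**Order of events.** Consent and randomisation come first, then the two-week Fitbit baseline, then app training and use from week 3. App use is a post-randomisation variable.

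**Algebra.** Let C be condition, A app use, M the mediator and Y well-being. Let s be the effect of C on A (in SD), d that of A on M, p that of C on M outside A, and b that of M on Y.

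- Whole effect of C on Y through M: (p + d·s)·b.
- A in both equations: the M regression gives p for condition, so the reported product is p·b. The omitted part is d·s·b.
- A in the outcome equation only: the M regression gives p + d·s, so nothing is omitted.

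**Numbers, case 1.** Assumed, not from the documents: p = 0.3, d = 0.4, b = 0.4. An unmeasured motivation factor has path 0.4 to app use and 0.4 to well-being but none to the mediator.

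| Shift s (SD) | Whole: (0.3 + 0.4s) × 0.4 | Adjusted: 0.3 × 0.4 | Returned |
|---|---|---|---|
| -0.3 | 0.072 | 0.120 | 167% |
| 0 | 0.120 | 0.120 | 100% |
| 0.3 | 0.168 | 0.120 | 71% |
| 0.8 | 0.248 | 0.120 | 48% |

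At every shift the outcome-equation-only version returns 100%, and the version with app use in neither equation returns 114%, because app use then confounds M and Y.

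**Numbers, case 2.** Motivation also affects the mediator (assumed path 0.3). The adjusted coefficient of C on M becomes 0.3 - 0.4 × 0.3 × s, and that of M on Y becomes 0.494. At s = 0.3 this gives 0.264 × 0.494 = 0.130 against 0.168, or 78%. At s = 0.8 it gives 0.204 × 0.494 = 0.101 against 0.248, or 41%. At s = 0 it is 123%. The outcome-equation-only version returns 0.494 / 0.4 = 123% throughout, and the version with app use in neither returns 134% throughout.

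**Accuracy at n = 66 (31 vs 35).** A serial model with app use first gives the same estimate as the outcome-equation-only version, because in least squares its two paths into M add up to the unadjusted effect of C on M. Simulated root-mean-square errors (10,000 runs per cell), adjusted versus serial:

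| Shift | Case 1 | Case 2 |
|---|---|---|
| 0 | 0.112 vs 0.118 | 0.140 vs 0.154 |
| 0.3 | 0.125 vs 0.127 | 0.143 vs 0.159 |
| 0.8 | 0.175 vs 0.140 | 0.207 vs 0.179 |

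The alternative is no more accurate at small shifts and is better at large ones.

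**Would a test of app use by arm settle it?** With 31 and 35 posttest completers, the standard error of the arm difference is √(1/31 + 1/35) = 0.247 SD and the 95% half-width is 1.96 × 0.247 = 0.48 SD. Power is 22% for a 0.3 SD shift and 51% for 0.5 SD. A non-significant difference would not rule out a shift that matters.

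**The case against.** **The loss depends on four conditions.** Condition must be the predictor, app use must be in the mediator equation, condition must shift app use, and app use must affect the mediator. The plan states neither of the first two, and the last two are plausible but not shown. This stands, and it limits the point. If the predictor is change in support or activity, adjusting for app use is defensible. If app use is in the outcome equation only, the path is not lost. If condition does not shift app use, nothing is omitted.

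**The arms may have used the app equally.** Both got daily reminders and equal researcher contact. A reader might infer that overall use must differ because the social features do. The documents do not support that: only use of the social features differs by design.

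**The adjustment does some good.** App use may confound mediator and outcome. In case 2 with no shift, the adjusted model returns 123% and the model without app use 134%. This stands, so simply deleting app use is not the remedy.

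**A serial model may be misordered.** Steps and app use cover the same weeks, and flowers grow as step goals are met, so activity can drive app use. This also stands for physical activity. It would trouble any model that includes app use, and it is why a serial model should be optional.

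**Isolating the path outside app use could be a legitimate aim.** It could, but the plan does not state it.

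**Conclusion.** The point holds in conditional form. Under the stated covariate rule, a mediation model with condition as predictor and app use in its mediator equation reports only the path outside app use. That both conditions apply is an inference: the covariate statement reads most naturally as both equations, and the predictor is not given.

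The size and even the direction are unknown here. Under the case 1 paths the adjusted model returns 100%, 71% and 48% of the indirect effect at shifts of 0, 0.3 and 0.8 SD; a negative shift would make it too large. These percentages illustrate the mechanism and do not estimate the error in this trial.

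Two stronger readings should be resisted. One is that the mediation results are shown to be wrong; the documents give no app-use figures by arm. The other is that the condition-by-time comparisons are contaminated too. Those models control for covariates that the section does not list, and app use is named only for the mediation models. The matter is worth correcting because it governs what the mechanism claim means and the data to resolve it exist. Confidence is medium.

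**What to change.** 1. State, for each mediation model, the predictor, the variables in the mediator equation and in the outcome equation, and one app-use measure available in both arms (for example, days on which the app was opened).
2. Where condition is the predictor, adjust the mediator equation for pretest or baseline variables only. Report the indirect effect with app use kept in the outcome equation only, and with app use in neither equation, beside the fully app-use-adjusted estimate. Label the last as the path outside app use.
3. Report app use by arm with a confidence interval, not only a significance test.
4. A serial model with app use first is optional. State its ordering assumption, which is uncertain for physical activity.

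**Cost.** A few lines of SAP text, a few extra model runs and one descriptive table. The Measures section says that app-usage data were collected electronically, so no new data are needed.

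**Limits.** Intervals will be wide at about 66 participants. None of these models removes unmeasured confounding among app use, mediator and well-being, and at small shifts the alternatives are not more accurate than the adjusted model. The gain is that the reader sees which effect is reported and how far it depends on the handling of app use.
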